Ketamine is an antagonist of the N-methyl-D-aspartate (NMDA) receptor(14) and has repeatedly shown to be a safe, tolerable,(15) and effective means of treating depression, in particular TRD.(16) The therapeutic mechanisms of ketamine are not fully understood; however, ketamine is associated with changes in synaptic function and neuroplasticity, and these changes are correlated with a decrease in depressive symptoms(17). It has been theorized that ketamine's effectiveness, is in part because it, "...promotes a time-out from ordinary, usual mind, relief from negativity, and an openness to the expansiveness of mind..." (p. 191).(18) Although anecdotal, ketamine may theoretically aid in increasing openness and decreasing negative rigidity, core features of the HPM/OC phenotype and vital aspects of RODBT treatment. Ketamine's effects are fast-acting and transient, which has led to growing interest in combining ketamine with psychotherapy(17,18). Facilitating new neural connections make ketamine a powerful adjunct to existing therapy, and in particular might be amenable to

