The experimental research measures in this project will not directly benefit the participants, other than the knowledge that they are contributing to our understanding of the underlying factors that may cause treatment-resistance to previous treatments and may provide insight into a novel medication-enhanced psychotherapy and thus, there is a benefit of contribution to society. In the therapy portion of the project, it is also possible that participants may experience improved symptoms of depression, mood, anxiety, as well as reduced tendencies of HPM/OC. As part of the ketamine treatment, participants may also experience improved symptoms of depression and anxiety. There is a possible effect that the combination of ketamine and RO DBT will be especially beneficial in combination, although this is unknown, as it is a goal of the study to test the combined treatment. As mentioned above, measures are being taken to minimize any potential risks.

E Study Design

E1 Overview or Design Summary

Eligible patient (n=15) young adults will attend a baseline session where they will undergo an ERP neural assessment and fill out questionnaires. Then, participants will complete 4 weeks of ketamine and 4 months of RO DBT. Participants will start with 2 weeks of individual therapy (RODBT) to orient to therapy and infusion protocols. Then, participants will complete a 4-week course of twice weekly 40-minute ketamine infusions administered 6-24 hours prior to RO DBT psychotherapy (also when RO DBT group therapy will commence). Following completion of the 4-week ketamine-enhanced RO DBT, participants will complete another in-person session with an EEG and behavioral assessment. Next, participants will continue to complete RO DBT treatment of individual and group treatment for an additional 16 weeks. At the end of this treatment, participants will complete a third session where they will undergo an ERP neural assessment and fill out questionnaires. Participants will also complete self-reported questionnaires following each ketamine and RO DBT

session (4 weeks) and weekly self-reported questionnaires during non-ketamine RO DBT.

E2 Subject Selection and Withdrawal

2.a Inclusion Criteria

Young adults with treatment-resistant depression: Inclusion criteria:

- Males and females aged 18-65

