choose a door and the doors will remain on the screen until the participant chooses a door. Then a fixation mark is presented, followed by a feedback arrow: a green upward facing arrow indicates a correct guess (i.e., they won points), while a red downward facing arrow indicates an incorrect guess (i.e., they lost points). A fixation mark is then presented and then a screen that states, "Click for next round" is presented until a response is made. Behavioral responses will be recorded and EEG will be recorded during the task and used to measure the RewP. Participants will complete 6 minutes of resting state EEG where they will keep their eyes closed for 1 minute, followed by eyes open for 1 minute, for 6 consecutive minutes where they will be told to 'do nothing.' In total, the ERP portion of the task will take approximately 1.5 hours.

Following the ERP/EEG session, participants will meet with a researcher and complete a structured clinical interview, the Montgomery and Asberg Depression Rating Scale (MADRS) to assess current depressive symptoms. Participants will also complete the Mini International Neuropsychiatric Interview (MINI) as part of this clinical interview as well. This should take approximately 30 minutes.

Participants will then sit at a computer and complete online questionnaires on REDCap. Questionnaires will take approximately 20 minutes and can be completed at home as well. Questionnaires include:

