Acceptance and Action Questionnaire-II (AAQ-II): This measure assesses psychological inflexibility. Pathological Obsessive Compulsive Personality Scale (POPS): This measures personality traits related to the HPM/OC personality, including emotional overcontrol, perfectionism, rigidity. Social Connectedness Scale- Revised (SCS-R): This measure assesses the degree to which participants feel socially connected to others. UCLA Loneliness Scale Revised: This measures one's subjective feelings of emotional and social loneliness. Temporal Experience of Pleasure Scale (TEPS): This measure assesses anticipatory pleasure and consummatory or outcome pleasure. Patient Health Questionnaire – 9 (PHQ-9): This is a measure of depressive symptoms. Generalized Anxiety Disorder Questionnaire – 7 (GAD-7): This is a measure of anxiety symptoms. Quality of Life Questionnaire (QOL) – A 16-item measure for assessing quality of life in groups with chronic illness. Personal Need for Structure – This measure assesses the extent to which participants need structure in their daily lives. Social Safeness and Pleasure Scale – This measure assesses feelings of positive emotions and pleasure in social situations. Emotion Regulation Questionnaire (ERQ) – The Emotion Regulation Questionnaire (ERQ) was developed to measure two specific constructs related to emotion control: cognitive reappraisal and expressive suppression. The ERQ is a 10-item self-report measure employed to measure dispositional use of the emotion regulation strategies of emotional suppression and reappraisal. The items use a 7-point Likert scale with responses ranging from one (strongly disagree) to seven (strongly agree). Responses to Positive Affect (RPA) – (RPA; Feldman et al., 2008). The RPA is a 17-item measure rated on a 1 (almost never respond in this

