Using G*Power, power for Aim 1 (MDD symptoms) was based on a) a pilot of RODBT from the PI, b) Lynch et al. (2020),⁽⁹⁾ a multi-site RCT of RODBT in TRD and c) Zarate et al (2006)⁽³⁷⁾, an original RCT of ketamine in TRD. With $\alpha=.05$ and power of 80%, we would need a sample of 8 to detect an effect from RODBT, and $n=5$ with ketamine. For Aim 2, we used a) Baudinet et al (2021)⁽¹¹⁾ who tested RODBT change in behavioral flexibility and reward processing and b) a pilot of RODBT from the PI. With $\alpha=.05$ and power of 80%, we would need a sample of 5-15 participants to detect behavioral change in mechanistic process. Power for neural change in HPM/OC has not been computed because no previous studies have targeted HPM/OC with ketamine. However, our sample is similar to other medication-assisted psychotherapy pilot studies.

G2 Interim Monitoring and Early Stopping

This is part of Analysis 1a below. Specifically, side effects and symptoms will be monitored at each ketamine and RO DBT session for 4 weeks while they are running concurrently. If there are any issues with running a ketamine session and a psychotherapy session within 1-2 days of each other, protocols can be modified or stopped, if necessary.

G3 Analysis Plan

Analysis 1a: No analyses will be completed for H1a; qualitative data from session questionnaires regarding side-effects, symptoms and functioning will be continually monitored, to assess if there is a need to modify protocols. **H1b:** Using individual session data, ketamine will catalyze psychiatric symptom change in RODBT and ketamine-enhanced RODBT will be associated with decreasing trajectories of depressive symptoms. Analysis 1b: Multilevel linear modeling (MLM) with random intercepts and slopes will model trajectories of depressive symptoms across treatment.

Aim 2: Examine preliminary efficacy of ketamine-enhanced RODBT in engaging neural and behavioral mechanistic targets in young adults with

moderate to severe depression.

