H2a: Ketamine-enhanced RODBT will be associated with neural ERN reductions and neural RewP increases. Analysis 2a: Using baseline, mid- and post-treatment assessments, change in the ERN (and in a separate model, the RewP) will be assessed using a MLM. **H2b:** Ketamine-enhanced RODBT will be associated with behavioral cognitive flexibility, openness, reward responding and social functioning improvements. Analysis 2b: Using baseline, mid- and post-treatment assessments, change in behavioral mechanisms will, similar to Analysis 2a, be assessed using a MLM.

G4 Statistical Methods

See above

G5 Missing Outcome Data

If missing outcome data exists, that participant will be excluded for that analysis. Of note, when modeling data, missing data does not mean the participant can be excluded.

H References

1. Lynch TR. Radically Open dialectical behavior therapy: Theory and practice for treating disorders of overcontrol. Oakland, CA: Context Press; 2018.

-

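### Analysis 1b does not say whether the Visit 1 PHQ-9 enters, and a single linear slope would miss most of an early fall in depression scores with or without it

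*Combined protocol and SAP*

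**What the plan says.** - **Analysis 1b (G3).** H1b is framed as "Using individual session data, ketamine will catalyze psychiatric symptom change in RODBT". The analysis is one sentence: "Multilevel linear modeling (MLM) with random intercepts and slopes will model trajectories of depressive symptoms across treatment". It names no scale, time zero, baseline term or phase term, and G4 adds nothing.
- **Analyses 2a and 2b (G3).** Both name their time points: "Using baseline, mid- and post-treatment assessments, change in the ERN" and "Using baseline, mid- and post-treatment assessments, change in behavioral mechanisms will".
- **Visit 1 (F2).** Two depression measures are taken before study treatment: "Patient Health Questionnaire – 9 (PHQ-9): This is a measure of depressive symptoms" and "the Montgomery and Asberg Depression Rating Scale (MADRS) to assess current depressive symptoms". Only the PHQ-9 is repeated at sessions, so it is the evident outcome for 1b.
- **Session scores.** E1 states: "Participants will also complete self-reported questionnaires following each ketamine and RO DBT" sessions, and adds weekly questionnaires in RO DBT without ketamine. F2 puts the PHQ-9 at each infusion (before or after is not stated), after each therapy session in the ketamine phase, and weekly afterwards. F2 lists none in the two weeks of individual RO DBT that precede the first infusion; the weekly wording in E1 could cover them.
- **Expected pattern (B1).** "Ketamine's effects are fast-acting and transient". B1 also says the session data should show when the largest drop occurs.

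**The concern.** H1a has no formal analysis, so Analysis 1b carries the whole efficacy claim of the primary aim. Random intercepts and slopes with no phase term or curve describe one straight line per participant.

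Every session PHQ-9 comes after some study treatment: at least one therapy session and possibly the first infusion. A line fitted to those scores starts from a level that may already have fallen, and its slope describes only what follows. A rapid early fall followed by a plateau is close to what the protocol predicts for ketamine. It is also the pattern that a single slope reports worst, so a treatment that works as hypothesised could show little or no decreasing trajectory. Two analysts could also choose different time zeros and report different primary results from the same data.

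**Working it through.** **The plan's own figures.** G1 gives n=8 (RO DBT) and n=5 (ketamine) for Aim 1 at alpha .05 and 80% power. It states no effect size, SD, sidedness or test, so these cannot be reproduced. Nothing below depends on them.

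**Step 1: what a straight line does with an early fall.** Assumed: Visit 1 mean PHQ-9 of 18, a fall D before the first session score (week 2.1), then 0.25 points per week to a last score at week 15.5.

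- True fall = D + 0.25 × (15.5 − 2.1) = D + 3.35.
- Session scores only: the slope is −0.250 for every D, so the modelled fall is always 3.35.
- Visit 1 as one more point on the line: see the table.

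| D | True fall | Session-only fall | Slope with Visit 1 | Fall implied by that line |
|---|---|---|---|---|
| 0 | 3.35 | 3.35 | −0.243 | 3.76 |
| 2 | 5.35 | 3.35 | −0.271 | 4.20 |
| 4 | 7.35 | 3.35 | −0.299 | 4.63 |
| 6 | 9.35 | 3.35 | −0.327 | 5.06 |

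Share of D recovered by adding Visit 1 = (implied fall − 0.25 × 15.5) / D. For D=4 this is (4.63 − 3.875) / 4 = 0.19. Across D of 2 to 6, an end at week 16 or week 22, and a lead-in scored or not, the share is about 11 to 20%.

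A random-intercept-and-slope simulation (15 participants, 60 runs, D=4) agrees. The slope is −0.250 with session scores only and −0.297 with Visit 1 added. With a separate step after Visit 1, the slope is −0.250 and the step −3.3 at week 0. The modelled fall by the first session score is then 3.3 + 0.25 × 2.1, about 3.9 points, against a true 4.

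**Step 2: effect on power.** Assumed: N=15, two-sided .05, slope SD 5/16 per week, residual SD 2.5 (the intercept SD cancels), total fall 6 points by week 16. There are 16 scores from week 2.25 to week 6, then weekly scores in weeks 7 to 16. The early share falls before the first of these scores, and the rest is spread evenly over weeks 0 to 16. Each participant's least-squares slope is tested by a one-sample t-test, a two-stage stand-in for the MLM.

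- **Session slope, half early.** Mean slope 3/16 = 0.1875, or 3.0 points over 16 weeks. The sum of squares of the times is 438.5. SD = √((5/16)² + 2.5²/438.5) = 0.3345; SE = 0.3345/√15 = 0.0864; noncentrality 0.1875/0.0864 = 2.17. Power is about 52% (53% by simulation).
- **The same with lead-in scores at weeks 1 and 2**, the early fall coming at the first infusion. Sum of squares 494.4, SE 0.0858, mean slope 0.249 (4.0 points over 16 weeks), noncentrality 2.90. Power is about 77%.
- **Mean of the last four scores (weeks 13 to 16, mean 14.5) minus Visit 1.** Expected fall 3 + 3 × 14.5/16 = 5.72. SD = √((14.5 × 5/16)² + 2.5² × 1.25) = 5.32; SE = 1.375; noncentrality 4.16. Power is about 97%.

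Power by early share, from the same formulas:

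| Total fall, early share | Slope, no lead-in scores | Slope, lead-in scored | End minus Visit 1 |
|---|---|---|---|
| 6, none | 98% | 98% | 96% |
| 6, quarter | 86% | 92% | 96% |
| 6, half | 52% | 77% | 97% |
| 6, three quarters | 17% | 52% | 98% |
| 4, none | 77% | 77% | 69% |
| 4, half | 27% | 44% | 73% |

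If the gradual part instead begins only at the first session score, the half-early 6-point slope power is about 65% without lead-in scores and 81% with them.

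**Step 3: the price of using Visit 1.** Suppose there is no treatment effect but Visit 1 scores are 2 points too high through selection on severity (assumed). The noncentrality is 2/1.375 = 1.45, and the contrast is significant in about 27% of trials. For 3 points it is about 53%.

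**The case against.** A reader might infer that the plan excludes Visit 1, so that the early fall is certain to be lost. The documents do not support that. The session wording sits in the hypothesis; the analysis sentence says only that trajectories are modelled over treatment. E1 also calls the baseline visit a session, so Visit 1 could count as session data.

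A reader might also infer that the first score always follows an infusion. That is open too: if the lead-in is scored, about two PHQ-9 values precede ketamine and the fast fall lies inside the series. The problem then shrinks but remains (77% against 97% in the half-early case).

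Nor is the Visit 1 PHQ-9 the only depression score before study treatment. The MADRS is taken at the same visit, and background medication may continue. Questionnaires are repeated at the mid- and post-treatment visits, so a PHQ-9 change from baseline can be computed from planned data. The information is collected; what is missing is its place in the primary analysis.

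Three further objections stand:

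- In a single-arm trial that enrols on severity, a baseline contrast counts regression to the mean as improvement. A session-only slope is less exposed to this.
- The power comparison uses a simple end-minus-baseline contrast as a stand-in for the model-based change proposed below.
- This is a 15-person pilot with no decision rule tied to the slope, which limits the consequences.

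**Conclusion.** The concern holds in conditional form. Analysis 1b does not say whether the Visit 1 PHQ-9 enters. With session scores only, a fall before the first score is absorbed by the intercept; with Visit 1 added to a single line, only about 11 to 20% of it is recovered in the scenarios tried. So naming baseline is not enough on its own; the form of time matters as well.

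For a 6-point fall with half early, the session slope implies about 3.0 points with about 53% power, or about 4.0 points with about 77% if the lead-in is scored, against about 5.7 points and 97% for end minus baseline. These figures rest on assumed SDs, total fall, early share and schedule, none of which the plan gives. The end of treatment is also unclear: F2 describes about 16 weeks of RO DBT, while E1 adds 16 weeks after the ketamine phase (2 + 4 + 16 = 22), and these passages must be reconciled. With no early fall the slope is as good or better, so it should be kept and supplemented. This is an inexpensive improvement worth making before analysis.

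**What to change.** In Analysis 1b:

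1. Name the PHQ-9 as the outcome and enter the Visit 1 score as the week-0 outcome.
2. Replace the single line with phase terms: baseline and lead-in, ketamine phase, RO DBT only.
3. Report model-based change from Visit 1 to the end of the ketamine phase and to the end of RO DBT, with 95% intervals, beside the slope.
4. State whether the lead-in is scored, and whether infusion-day scores are taken before or after the infusion.
5. Describe the change from Visit 1 as uncontrolled. If lead-in scores exist, also report change from the last score before the first infusion, which is less exposed to regression to the mean.

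The cost is a few sentences in the plan; Visit 1 is already collected. The downsides are extra model terms with 15 participants, a Visit 1 score taken in a different setting from session scores, and the regression to the mean that item 5 addresses only in part.

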facilitating change in RODBT. Ketamine has demonstrated change in neural reward responding and has improved social functioning in depression,(18) both of which are central to the HPM/OC phenotype. Indeed, work from key personnel on this proposal demonstrate that in adults with TRD, ketamine infusions demonstrate response-dependent changes in functional connectivity in the anterior cingulate cortex (ACC), default mode network and limbic/reward structures, including the amygdala and nucleus accumbens.(19) Of note, the ACC has been repeatedly implicated in performance and error-monitoring (e.g., HPM/OC),(20) and is where the EEG-based neural marker, the ERN is thought to originate(21) while the nucleus accumbens is a reward structure where the RewP is theorized to originate from.(22) Together, ketamine may provide initial, fast-acting change to catalyze and facilitate longer-term neural and psychiatric change in RODBT in individuals with TRD. Ketamine-assisted psychotherapy is still in early stages of study,(18) so the current proposal will take a 'deep-dive' examination of feasibility and session-by-session change in ketamine- enhanced RODBT. This will allow us to a) test whether ketamine acts as a catalyst to RODBT, increasing openness and flexibility for RODBT therapy sessions and b) examine trajectories of change across the treatment, assessing when ketamine induced plasticity is associated with the largest drop in psychiatric symptoms (Aim 1). Additionally, repeated EEG neural assessments (baseline, post-ketamine and post-RODBT) will allow us to a) test whether a shorter course of RODBT, boosted with concurrent ketamine (8 weeks) is enough to enact neural change, or, whether the full course of ROBDT (16 weeks) is necessary to elicit neural change and b) assess whether targeting the neural and behavioral mechanism of HPM/OC is directly associated with improving MDD symptoms and functioning (Aim 2).

B2 Rationale for this Study

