unlimited time for the participant to consider whether they would like to participate in the study and a research assistant will notify the participant they can contact the research team if they would like to potentially participate in the future (they may have to re-complete the phone screen at that future time). If the person is still interested, the research team will schedule an in-person session.

The consent process will take place in person at Washington University in St. Louis Department of Psychiatry in a private room with a research team member. The consent process will include providing ample time for the young adult to read/review the consent form. This consent will consent for the experimental sessions and the free ketamine and therapy portion. There is no randomization: if an potential patient participant is interested in the free ketamine/therapy, they can participate in that until we have 15 participants in the therapy portion. A trained research assistant will also discuss the procedures of the study and will answer any questions the participant may have prior to signing. Research team members will remind participants that their participation is completely voluntary and they can choose to withdraw at any time.

2.d Early Withdrawal of Subjects

Participants can withdraw at any point if they desire. Participants in need of higher levels of care will be withdrawn by the PI if medically/psychologically unstable or if they express active suicidal ideation.

2.e When and How to Withdraw Subjects

Participants in need of higher levels of care will be withdrawn by the PI at any point if medically/psychologically unstable or if they express active suicidal ideation and need to be hospitalized. If a participant desires to withdraw, as soon as they inform the study team, the team will remove the participant from current and future study procedures.

2.f Data Collection and Follow-up for Withdrawn Subjects

Data will not be collected for withdrawn subjects once they withdraw. Follow-up for withdrawn subjects will not be done, unless the patient reaches out to us and would like to continue the therapy or study. At this point they would sign another consent form to agree to their continued participation.

F Study Procedures

F1 Screening for Eligibility

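### G5 gives two conflicting rules for missing outcome data, so the plan does not exclude deleting whole participants from the multilevel models

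*Combined protocol and SAP*

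**What the plan says.** G5 (Missing Outcome Data) has two sentences. The first is "If missing outcome data exists, that participant will be excluded for that analysis". The second is "Of note, when modeling data, missing data does not mean the participant can be excluded". G4 only points back to the preceding text.

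G3 specifies three analyses, all MLMs:
- Analysis 1b: "Multilevel linear modeling (MLM) with random intercepts and slopes will model trajectories of depressive symptoms across treatment".
- Analysis 2a: "change in the ERN (and in a separate model, the RewP) will be assessed using a MLM", using baseline, mid- and post-treatment assessments.
- Analysis 2b: "change in behavioral mechanisms will, similar to Analysis 2a, be assessed using a MLM".

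No statistical analysis is planned for Hypothesis 1a. Section B1 adds an aim with no model in G3: to "assess whether targeting the neural and behavioral mechanism of HPM/OC is directly associated with improving MDD symptoms and functioning".

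On withdrawal, 2.d says "Participants in need of higher levels of care will be withdrawn by the PI if medically/psychologically unstable or if they express active suicidal ideation". Section 2.e has such participants "withdrawn by the PI at any point if medically/psychologically unstable or if they express active suicidal ideation and need to be hospitalized". The two sections word the suicidal-ideation trigger differently and should be reconciled; this point does not depend on which applies. Under 2.f, no data are collected after withdrawal unless the participant returns and consents again.

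**The concern.** The two sentences give different analysis sets, and nothing else in the plan chooses between them. G3 names no estimation method, no missing-data assumption and no minimum number of scores. An analyst could delete incomplete participants or keep them, claim compliance either way, and make the choice after seeing the data.

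Two features of this trial make the choice matter. First, the symptom outcome is collected on many occasions, so a rule triggered by any missing value would be triggered often. Second, some missing data will follow directly from worsening, because unstable participants are withdrawn. The scores they gave beforehand are then the only planned symptom scores on them. Deletion would remove those scores from the analysis of depressive trajectories, in a single group of 15 with no control arm to show the effect.

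**Working it through.** G5 states no figure to reproduce. The only input the documents fix is n = 15 (E1). The rest is counted from the schedule or assumed, as marked.

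**1. Which analyses can sentence 1 govern?** If sentence 2 governs models, it covers 1b, 2a and 2b, which is every analysis in G3. Sentence 1 is then left with a participant who has no value at all for an outcome, or with the unmodelled association in B1. G5 names neither. If sentence 1 is given effect on the named analyses, it deletes participants from the MLMs.

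**2. PHQ-9 forms per participant.** Analysis 1b uses session data, and the PHQ-9 is the depression measure collected at sessions (F2). The counts come from E1 and F2.

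| Component | Low | High |
|---|---|---|
| Baseline | 1 | 1 |
| Two orientation weeks, weekly | 2 | 2 |
| Infusions, 2 a week for 4 weeks | 8 | 8 |
| RO DBT sessions in those 4 weeks (individual only / individual and group) | 4 | 8 |
| Weekly forms after ketamine | 10 | 16 |
| Mid and post visits, if counted separately | 0 | 2 |
| Total | 25 | 37 |

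The 10 is 16 − 2 − 4, from the Therapy text in F2 (about 16 weeks of RO DBT in all). The 16 comes from E1 (16 further weeks after the ketamine phase). Those two passages need reconciling.

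**3. Expected participants kept if any missing form deletes the participant.** Kept = 15 × (1 − p)^k, with p an assumed, independent miss rate per form.

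| p | k = 25 | k = 37 | k = 3 (Analyses 2a, 2b) |
|---|---|---|---|
| 1% | 11.7 | 10.3 | 14.6 |
| 2% | 9.1 | 7.1 | 14.1 |
| 5% | 4.2 | 2.2 | 12.9 |

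For example, 15 × 0.98^25 = 15 × 0.603 = 9.1. If misses cluster within person, more are kept. With a beta-binomial at p = 5% and an assumed intraclass correlation of 0.1 (a = 0.45, b = 8.55), kept = 15 × B(a, b + k)/B(a, b) = 8.0 at k = 25 and 7.0 at k = 37.

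**4. Precision.** For a mean change with unchanged SD, the ratio of 95% interval widths with m participants against 15 is (t₀.₉₇₅,ₘ₋₁/√m) ÷ (t₀.₉₇₅,₁₄/√15), where the denominator is 0.554.
- m = 14: 0.577/0.554 = 1.04
- m = 13: 0.604/0.554 = 1.09
- m = 12: 0.635/0.554 = 1.15

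**5. Direction.** Let M be the mean change in all 15, E the mean in the k excluded and K the mean in those kept. From 15M = kE + (15 − k)K it follows that K − M = [k/(15 − k)] × (M − E). The factor is 1/14 = 0.07, 2/13 = 0.15 and 3/12 = 0.25 for k = 1, 2 and 3. Improvement is a negative change. If those excluded did worse than average (E > M), then K < M and improvement is overstated. If loss is unrelated to outcome, the expected shift is zero. If early improvers are lost, the sign reverses. The documents give neither k nor E, so the size stays open.

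**The case against.** The strongest reply is that sentence 2 is the specific exception for models, every specified analysis is a model, and the specific rule prevails. This largely stands: it is the more natural reading. Sentence 1 can also be given harmless work, such as dropping someone with no usable ERN at all. But G5 does not say so, and sentence 1 is worded as a general rule.

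A reader might infer that the plan is to delete incomplete participants. The documents do not support that; they permit deletion without prescribing it. Nor would deletion discard a participant's data from the study: sentence 1 is limited to the analysis concerned, so the scores could still enter other models.

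It can also be said that dropouts are not wholly lost. The Therapy text in F2 has the team contact them for an interview on their experience and perceived outcomes. That is correct, but no PHQ-9 is mentioned there, so it does not supply the missing trajectory.

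Finally, the miss rates are assumed, and independence gives the harshest count for a given rate. That stands, which is why the clustered result is shown beside it. Any figure for the bias would likewise rest on an assumed loss mechanism, so none is offered.

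**Conclusion.** The concern holds as an ambiguity in a stated rule and should be fixed. Confidence is high that the text permits both readings. It is moderate that deletion would overstate improvement in depressive symptoms, and that is conditional on sentence 1 being applied and on loss following worsening. The size of any such bias cannot be derived from the documents. The precision loss of about 4%, 9% and 15% follows from n = 15 alone, for a simple mean change with unchanged SD. The numbers kept under the any-missing-form rule depend on the assumed miss rate and on independence. For Analyses 2a and 2b, with three assessments, the loss from missed visits is smaller, and no direction of bias is claimed for ERN or RewP.

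**What to change.** Delete sentence 1 and replace G5 with a single rule, for example:

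> All participants with at least one value of the outcome are included. MLMs are fitted by REML to all available observations, including those before withdrawal, under missing at random. No participant is deleted for missed visits or forms.

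Add that any analysis other than an MLM, such as the association described in B1, states its own missing-data rule. Report withdrawals by reason and time of last score, so that readers can judge whether missing at random is credible. The rule cannot recover worsening that was never recorded before withdrawal, and that table would help show where this may have happened.

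The cost is a few sentences of wording and a short withdrawal table. Visits, treatment and sample size do not change. If sentence 2 was always the intention, this only writes it down.
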